#### **Sensitivity Analysis:**

No formal normality assumption tests will be performed for this sensitivity analysis (Table 24).

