16.2. Sample Size Determination

Interim Analysis will be conducted by an independent DMC after 18-week 6MWD data are available from 75 patients. The purpose of the interim analysis is to stop the trial for an early efficacy or futility conclusion or to continue the trial to 150 or 188 - patients (total randomized is higher to account for an anticipated 20% dropout rate). Group sequential early stopping criteria and sample size re-estimation methodology are further described in the statistics section of this protocol. They are constructed to control overall type 1 error at 0.025, 1-sided. Simulations assuming true underlying mean treatment difference in 6MWD ranging from 30-70 meters and standard deviations from 50 to 75 meters yielded >87% power for all cases except the most extreme case (mean difference 30 meters and SD 75), for which power was ~71%.

Subjects who do not comply with the required device adherence, as well as who do not meet the study entry criteria at Week 2, will be withdrawn from the study.

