16.3.5. Handling Missing Data

Missing data imputation for primary endpoint:

For primary analysis, i.e. change from baseline at Week 18, missing data will not be imputed.

The following missing data imputation techniques will be employed for sensitivity analyses of primary endpoint.

- 1) Last Observation Carry Forward (LOCF) approach will be applied for subjects not withdrawing trial due to adverse events, for subjects withdrawing trial due to adverse events (including deaths), worst value (for e.g. zero for 6MWD) will be assigned at EOS visit.
- 2) Worst-case imputation approach I (i.e. impute the missing value for a subject with worst value (within the subject) for all subjects who withdraw prematurely for any reason. The value of zero for 6MWD will be imputed for all deaths.
- 3) Worst-case imputation approach II (i.e., impute the missing value for a subject in the active and Placebo dose group by the worst result of all subjects with non-missing assessments in their respective assigned dose groups). The value of zero for 6MWD will be imputed for all deaths.
- 4) Worst-case imputation approach III (i.e. impute the missing value for a subject in the active dose group by the worst result of all subjects with non-missing assessments in the same active dose groups and impute the missing value for a subject in placebo group by his/her last available assessment prior to the missing assessment. The value of zero for 6MWD will be imputed for all deaths.

Missing data imputation for secondary endpoint:

For all the other efficacy endpoints, the last observation carry forward (LOCF) approach will be used in handling the missing data as that used in the EARLY study ([Galiè 2008](#)).

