#### **Analysis of Non-Normal Data:**

In case of normality issues, the analysis will be performed using van Elteren test for stratified response (change from baseline).

The SAS code applied as follows:

```
Proc Npar1way data=data;
```

```
  Strata strata;
```

```
  Class treatment;
```

```
  Var change;
```

```
Run;
```

In case, we encounter normality issues, the results needs to be interpreted accordingly.

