**Table 24: Sensitivity Analysis**

No.	Sensitivity Analysis
1	Primary analysis on Per Protocol Population
2	Primary Analysis on Modified Intention To Treat Population
3	Analysis will be performed with Last Observation Carry Forward (LOCF) approach will be applied for subjects not withdrawing trial due to adverse events, for subjects withdrawing trial due to adverse events (including deaths), worst value (zero for 6MWD) will be assigned at EOS visit.  The analysis will be performed on ITT population.
4	Analysis will be performed with worst-case imputation approach I (i.e. impute the missing value for a subject with worst value (within the subject) for all subjects who withdraw prematurely for any reason. The value of zero for 6MWD will be imputed for all deaths.

No.	Sensitivity Analysis
	The analysis will be performed on ITT population.
5	
Analysis will be performed with worst-case imputation approach II (i.e., impute the missing value for a subject in the active and Placebo dose group by the worst result of all subjects with non-missing assessments in their respective assigned dose groups). The value of zero for 6MWD will be imputed for all deaths.
 
The analysis will be performed on ITT population.

6	
Analysis will be performed with worst-case imputation approach III (i.e. impute the missing value for a subject in the active dose group by the worst result of all subjects with non-missing assessments in the same active dose groups and impute the missing value for a subject in placebo group by his/her last available assessment prior to the missing assessment. The value of zero for 6MWD will be imputed for all deaths.
 
The analysis will be performed on ITT population.

7	Change from Baseline in 6MWD analyzed using the same model as primary for all subjects completing the 18 weeks treatment in ITT and mITT population.
8	Change from baseline (defined as week 1 assessment) in 6MWD analyzed using the same model as primary on ITT population
9	Change from baseline analyzed using the same model as primary for all subjects on IV/SC prostacyclin +/- orals in ITT population.
10	The Change from baseline analyzed using the same model as primary on ITT population for all subjects on one oral treatment (no IV, Inhaled and SC) of either prostacyclin or Endothelin Receptor Antagonists (ERAs) or Phosphodiesterase Inhibitors (PDE 5 Inhibitors)

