**Table 25: Summary of Primary Analysis**

Variable	Model	Population	Factors	Primary /Sensitivity	Imputation technique /algorithm
The Change from baseline in 6MWD	MMRM	ITT	Treatment Group, Visit, Treat*Visit Prostanoid Usage and Baseline 6MWD	Primary	No Imputation
The Change from baseline in 6MWD	MMRM	PP & mITT	Treatment Group, Visit, Treat*Visit Prostanoid Usage and Baseline 6MWD	Sensitivity	No Imputation
The Change from baseline in 6MWD	ANCOVA at week 18	ITT	Treatment Group, Prostanoid Usage and Baseline 6MWD	Sensitivity	LOCF and Worst value to all subjects who withdraw prematurely due to AE or death
The Change from baseline in 6MWD	ANCOVA at week 18	ITT	Treatment Group, Prostanoid Usage and Baseline 6MWD	Sensitivity	Worst case Imputation Approach (I, II & III)
The Change from baseline in 6MWD	ANCOVA at week 18	ITT	Treatment Group, Prostanoid Usage and Baseline 6MWD	Sensitivity	No Imputation
Change from Baseline in 6MWD	MMRM	ITT (all subjects completed 18 weeks of treatment)	Treatment Group, Visit, Treat*Visit Prostanoid Usage and Baseline 6MWD	Sensitivity	No Imputation
Change from Baseline in 6MWD	MMRM	mITT (all subjects completed 18 weeks of treatment)	Treatment Group, Visit, Treat*Visit Prostanoid Usage and Baseline 6MWD	Sensitivity	No Imputation
Change from baseline (defined as week 1 assessment) in 6MWD analyzed using the same	MMRM	ITT	Treatment Group, Visit, Treat*Visit Prostanoid Usage and Baseline 6MWD	Sensitivity	No Imputation

Variable	Model	Population	Factors	Primary /Sensitivity	Imputation technique /algorithm
model as primary.					
Change from baseline in 6MWD for subjects with PAH SPECIFIC THERAPIES (PHST) [PHST] and algorithm to filter the Prostacyclin IV and Oral therapy.	MMRM	ITT (all subjects on IV/SC prostacyclin +/- orals)	Treatment Group, Visit, Treat*Visit Prostanoid Usage and Baseline 6MWD	Sensitivity	No imputation
Change from baseline in 6MWD for subjects with PAH SPECIFIC THERAPIES (PHST) [PHST] and algorithm to filter for oral treatments.	MMRM	ITT (all subjects on one oral treatment of either prostacyclin or Endothelin Receptor Antagonists (ERAs) or Phosphodies terase Inhibitors (PDE 5 Inhibitors)	Treatment Group, Visit, Treat*Visit Prostanoid Usage and Baseline 6MWD	Sensitivity	No imputation

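### Sensitivity analysis 3 (and 4, for deaths) fits raw-change ANCOVA to 6MWD values set to zero, with no rank-based companion, so a few zeros can dominate the result

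*SAP*

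**What the plan says.** The primary analysis is an MMRM on the ITT set with no imputation (SAP 7.3.1 and Table 25; Protocol 16.3.5). SAP Table 24 then lists four missing-data sensitivity analyses.

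- **Item 3:** LOCF, except that for subjects who withdraw because of an adverse event, deaths included, the "worst value (zero for 6MWD) will be assigned at EOS visit". Protocol 16.3.5 has the same rule: "worst value (for e.g. zero for 6MWD) will be assigned at EOS visit".
- **Items 4 to 6:** zero for deaths only. Other missing values take the subject's own worst value (item 4), the worst value in the subject's group (item 5), or the group's worst on active and the last available value on placebo (item 6).

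Table 25 describes item 3 as "LOCF and Worst value to all subjects who withdraw prematurely due to AE or death". It assigns items 3 to 6 to a Week 18 ANCOVA on change from baseline with treatment, prostanoid use and baseline 6MWD. The sentence above Table 24 reads "No formal normality assumption tests will be performed for this sensitivity analysis".

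Two rank methods appear elsewhere in 7.3.1. One is the fallback for the primary analysis: "In case of normality issues, the analysis will be performed using van Elteren test for stratified response (change from baseline". The other is the ranked MMRM of item 12, which depends on violated assumptions and which Table 25 lists with no imputation. Neither is applied to the zero-imputed data.

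**The concern.** A zero walk gives a change of exactly minus the baseline. With entry walks limited to 100-450 m (Protocol 9.3, criterion 6), such a subject usually lies several planning SDs from everyone else. This non-normality is foreseeable, because the imputation rule creates it. Least squares then gives each zero the weight of its distance in metres, so a few subjects can supply about half of the residual variance.

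Items 3 to 6 are the planned checks on an MMRM that imputes nothing. If item 3 comes out non-significant, the reader cannot tell whether the effect is fragile or whether the model has been overwhelmed by a few outliers. If the zeros happen to fall more on placebo, the check can look better than the primary result for the same reason.

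**Working it through.** **1. The plan's own figures.** Protocol 16.2 says of the interim and re-estimation rules that "They are constructed to control overall type 1 error at 0.025, 1-sided". It states "Simulations assuming true underlying mean treatment difference in 6MWD ranging from 30-70 meters and standard deviations from 50 to 75 meters yielded >87% power", except for "the most extreme case (mean difference 30 meters and SD 75), for which power was ~71" per cent.

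- Hwang-Shih-DeCani spending, gamma -3, at half information: 0.025 × (1 − e^1.5)/(1 − e^3) = 0.00456. The final boundary is 0.02288. These match 0.0046 and 0.0229.
- Fixed design at 30 m, SD 75, 75 per arm: 30/(75√(2/75)) = 2.449, and Φ(2.449 − 1.960) = 68.8%. Simulating the promising-zone design with non-binding futility gives 71.3% (zone 30-80%) or 69.5% (zone 57.2-80%), consistent with about 71%.
- Drop-out: 150/0.8 = 187.5, so 188, or 94 per arm.

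**2. Inputs for the zero-imputed analyses.** From the documents: 94 per arm, 1:1 allocation, one-sided 0.025, SD 50-75 m, effects from 30 m. Assumed, because the documents do not give them: mean baseline 300 m (range 200-350 m), baseline SD 80 m, and 1 to 9 zeros per arm.

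**3. Standard error.** Let q be the fraction of zeros per arm. The residual variance is about

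SD²(1 − q) + q(1 − q)D² + q × 80²,

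where D² averages the squared distance of a zero from the other subjects: (300² + 330²)/2 = 99,450 for a 30 m effect.

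- No zeros: 60√(2/94) = 8.8 m.
- Three per arm (q = 0.0319): 3,485 + 3,073 + 204 = 6,762; SD 82.2; SE 12.0 m. Share due to zeros: 1 − (8.8/12.0)² = 46%.
- Five per arm (q = 0.0532): 3,408 + 5,009 + 340 = 8,757; SD 93.6; SE 13.65 m. Simulation gives 13.7 m; share 1 − (8.8/13.7)² = 59%.

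**4. Power at 30 m, SD 60, equal zeros (simulation).**

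| Zeros per arm | ANCOVA SE (m) | ANCOVA | Rank test |
|---|---|---|---|
| 0 | 8.8 | 93% | 91% |
| 1 | 10.0 | 87% | not tabulated |
| 3 | 12.0 | 72% | 88% |
| 5 | 13.7 | 57% | 87% |
| 9 | 16.3 | 29% | 81% |

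- With zeros occurring at random at 5%: 58% against 84%. Across the variants run with about 5% zeros, ANCOVA lies at 51-58% and rank methods at 79-87%.
- ANCOVA with 0, 3 and 5 zeros per arm: 98%, 82%, 67% at SD 50; 78%, 57%, 45% at SD 75.
- ANCOVA with five zeros per arm, as mean baseline goes from 200 to 350 m: 74% down to 46%.

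**5. Larger effects, SD 60.** At 40 m with about 5% zeros, ANCOVA has 75-80% and rank ANCOVA 96-97%. At 50 m, ANCOVA keeps 98.5% with five zeros per arm and 92% with random 5% zeros. At random 10% zeros it falls to 75%, against 99% for van Elteren.

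**6. Type I error.** For ANCOVA it is 0.022-0.028 across zero rates of 0 to 10%.

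**7. Imbalance at a true 30 m.** One zero shifts an arm mean by about 300/94 = 3.2 m.

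- Five active, one placebo: (89 × 30 − 5 × 300)/94 − (−300/94) = 12.4 + 3.2 = 15.6 m. Power is 16% for ANCOVA and 75% for van Elteren.
- One active, five placebo: (93 × 30 − 300)/94 + 1,500/94 = 26.5 + 16.0 = 42.5 m. ANCOVA power is 98%.

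**8. The other rows.**

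- Item 4 at 40 m: ANCOVA 96% with one death per arm and 92% with three, against 97-98% for rank ANCOVA.
- Item 5 at 30 m, 19 non-completers per arm and no zeros: ANCOVA 43%, rank tests 64%.
- Item 6, same setting: ANCOVA about 0% with an estimate of -17 m, rank tests about 3%.

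**The case against.** Several points stand.

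- **The waiver.** A reader might infer that the sentence dropping normality tests is the defect. It is not. It drops formal tests only, does not rule out plots, and a Shapiro-Wilk test would repair nothing. Nor is the ANCOVA invalid, since its type I error is held.
- **Scope.** A reader might infer that zeros spoil all four imputation analyses. Adverse-event withdrawals become zero in item 3 alone. Items 5 and 6 are driven mainly by group-worst imputation of ordinary drop-outs: they lose most of their power with no zeros at all, and ranks recover only part of item 5 and almost nothing of item 6.
- **Consequence.** A reader might infer that an effective drug would usually fail its robustness checks. The documents set no pass/fail rule for these rows and leave them outside the testing hierarchy. The prior-study estimate quoted under SAP Table 22 is 69.6 m, well above the effects at which the loss is large. The direction is not fixed either: excess placebo zeros inflate the estimate.
- **Intent.** Worst-case analyses are meant to be harsh, and the SAP change history attributes the imputation rules with ANCOVA to FDA recommendations. Table 25 also has an unimputed Week 18 ANCOVA, which helps separate model from imputation. An estimate in metres is needed for comparison with the primary result, so the ANCOVA should not be removed.

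What survives is narrower. The plan claims power down to 30 m, and for effects of 30-40 m item 3 can lose much of its power to a few zeros while no planned rank analysis looks at the same data.

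**Conclusion.** The concern holds for item 3, and to a smaller degree for item 4 when deaths occur. With about five zeros per arm, raw-change ANCOVA has about 75-80% power at 40 m where rank ANCOVA has 96%, and about 50-58% at 30 m where rank methods have 80-87%. At 50 m the loss is small at that number of zeros. With no zeros the methods are nearly equal, so a rank analysis costs little power. Unequal zeros can move the estimate substantially in either direction.

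The figures depend on an assumed mean baseline of 300 m and on assumed numbers of deaths and adverse-event withdrawals. They were obtained by ranking the zero-imputed change. At a mean baseline near 300 m most zeros already fall at the bottom, so an explicit worst-rank score should behave similarly, but its power was not computed separately.

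The primary MMRM and its type I error are unaffected. This is an inexpensive improvement to the sensitivity plan and does not put the main conclusion in doubt.

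**What to change.** In SAP 7.3.1 and Tables 24 and 25, before unblinding:

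1. Keep the imputations and the Week 18 ANCOVA for items 3 to 6.
2. Add a worst-rank analysis for item 3, and for item 4 where deaths occur. Define the score explicitly: deaths lowest; under item 3, adverse-event withdrawals next lowest; all others ordered by their observed or imputed change.
3. Test the score by rank ANCOVA adjusted for prostanoid stratum and ranked baseline 6MWD, or by the van Elteren test. The SAP's existing van Elteren code cannot be reused unchanged, because it ranks change: a death with a baseline of 110 m scores -110 m and would rank above a survivor who lost 120 m.
4. State that for these two rows the rank result is the test of robustness and the ANCOVA difference in metres is the supporting estimate.

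No rank analysis is proposed for items 5 and 6, and deleting the waiver sentence would achieve nothing by itself. The cost is a short SAP edit, a few lines of code and one extra analysis per row. The drawback is that the added test result is not in metres.

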**Table 24: Sensitivity Analysis**

No.	Sensitivity Analysis
1	Primary analysis on Per Protocol Population
2	Primary Analysis on Modified Intention To Treat Population
3	Analysis will be performed with Last Observation Carry Forward (LOCF) approach will be applied for subjects not withdrawing trial due to adverse events, for subjects withdrawing trial due to adverse events (including deaths), worst value (zero for 6MWD) will be assigned at EOS visit.  The analysis will be performed on ITT population.
4	Analysis will be performed with worst-case imputation approach I (i.e. impute the missing value for a subject with worst value (within the subject) for all subjects who withdraw prematurely for any reason. The value of zero for 6MWD will be imputed for all deaths.

No.	Sensitivity Analysis
	The analysis will be performed on ITT population.
5	
Analysis will be performed with worst-case imputation approach II (i.e., impute the missing value for a subject in the active and Placebo dose group by the worst result of all subjects with non-missing assessments in their respective assigned dose groups). The value of zero for 6MWD will be imputed for all deaths.
 
The analysis will be performed on ITT population.

6	
Analysis will be performed with worst-case imputation approach III (i.e. impute the missing value for a subject in the active dose group by the worst result of all subjects with non-missing assessments in the same active dose groups and impute the missing value for a subject in placebo group by his/her last available assessment prior to the missing assessment. The value of zero for 6MWD will be imputed for all deaths.
 
The analysis will be performed on ITT population.

7	Change from Baseline in 6MWD analyzed using the same model as primary for all subjects completing the 18 weeks treatment in ITT and mITT population.
8	Change from baseline (defined as week 1 assessment) in 6MWD analyzed using the same model as primary on ITT population
9	Change from baseline analyzed using the same model as primary for all subjects on IV/SC prostacyclin +/- orals in ITT population.
10	The Change from baseline analyzed using the same model as primary on ITT population for all subjects on one oral treatment (no IV, Inhaled and SC) of either prostacyclin or Endothelin Receptor Antagonists (ERAs) or Phosphodiesterase Inhibitors (PDE 5 Inhibitors)
11	The Change from baseline analyzed using the same model as primary on ITT population for all subjects on at least two oral treatment (no IV, Inhaled and SC) of either prostacyclin or Endothelin Receptor Antagonists (ERAs) or Phosphodiesterase Inhibitors (PDE 5 Inhibitors)
12	
If the normality and homogeneity of variance assumptions are significantly violated, then the baseline and change from baseline parameters are first ranked separately, using the combined data from all treatment groups. Tied values will receive the mean value (midranks) of the corresponding ranks.
 
The primary analysis MMRM model on ranked values will be performed on ITT population.

13	Responder analysis for patients achieving $\geq 30$ meters 6MWD response from baseline at Week 18 will be performed using the proportions test on ITT population
14	Change from Baseline in 6MWD analyzed using the same model as primary for all subjects having concurrent use of INOpulse device with a continuous positive airway pressure (CPAP), bilevel positive airway pressure BiPAP, or any other positive pressure device.

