16.3. Efficacy Analyses

16.3.1. Primary Efficacy Endpoint

The primary endpoint is to evaluate the efficacy of iNO as measured by the placebo-adjusted change in 6-minute walk distance (6MWD) from baseline to 18 weeks. The average of the two 6MWDs at Week 2 (after run-in) will be used as the baseline value for analysis of data. The

6MWD at Week 2 should be obtained on all subjects, even if the subject does not qualify to enter into the treatment phase.

The primary statistical test for the primary endpoint will be performed using a repeated measures mixed model with the baseline stratification factor (i.e., the prostanoid usage status), - treatment arm, week, and treatment-by-week interaction as the main effects. As a covariate, baseline 6MWD assessment will be included in the model. In case the normality assumption is substantially violated (i.e., graphical assessment of residuals from the analysis model and the Shapiro-Wilk test statistic graphical assessment of the residuals from the analysis model and), the primary efficacy endpoint will be analyzed using the van Elteren test stratified by the prostanoid usage status. Least Squares mean differences, standard errors, 95% confidence intervals will be derived from the analysis model.

Exploratory analyses will be performed to evaluate the effects of demographics and baseline characteristics on the efficacy response with appropriate statistical methods. Subgroup analyses based on study drug usage, background therapies, demographics and baseline characteristics, as well as other study compliance status will be conducted. Additional statistical methods such as mixed effects model and Cochran–Mantel–Haenszel (CMH) test (for dichotomized response analysis) may be utilized in the exploratory analyses.

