16.3.3. Tertiary Endpoints

1. Change in health-related quality of life (using SF-36 version 2 health survey), with iNO as compared to placebo, from baseline to 18 weeks
2. Change in pulmonary hemodynamics (i.e., cardiac output [CO], cardiac index [CI], mean pulmonary artery pressure [mPAP], mean pulmonary capillary wedge pressure [mPCWP], systolic pulmonary artery pressure [sPAP], diastolic pulmonary artery pressure [dPAP], pulmonary vascular resistance [PVR], and oxygen saturation by pulse oximeter [SpO₂], mixed venous O₂, and right atrial pressure [RAP]) measured by right heart catheterization (RHC), with iNO as compared to placebo, from baseline to 18 weeks, in a subset of subjects (approximately 50), at selected sites
3. Change in echocardiogram measurements right ventricular function (including right ventricular fractional area change, systolic pulmonary artery pressure [sPAP], tricuspid annular motion/tricuspid annular plane systolic excursion, tricuspid annular systolic velocity, and Tei index) and left ventricular function (including left ventricular ejection fraction [LVEF], LV size, and improvement in LV early diastolic relaxation velocity), with iNO as compared to placebo, from baseline to 18 weeks, in a subset of subjects (approximately 50), at selected sites
4. Change in NT-proBNP, with iNO as compared to placebo, from Screening to 18 weeks
5. Change in Borg dyspnea score immediately following 6MWT, with iNO as compared to placebo, from baseline to 18 weeks
6. Change in 6MWD as related to degree of drug adherence, with iNO as compared to placebo, from baseline to 18 weeks
7. The number of subjects with unsatisfactory clinical response, with iNO as compared to placebo, from baseline to 18 weeks. Defined as: WHO Functional Class III or IV symptoms with no improvement in 6MWD
8. Number of subjects undergoing heart-lung or lung transplantation, number of subjects listed for transplantation, and deaths while awaiting transplantation, from baseline to 18 weeks
9. Medical resource utilization, with iNO as compared to placebo, from baseline from baseline to 18 weeks

For continuous (or numerical) response endpoints, the statistical analyses will be performed using the same method as that for the primary efficacy endpoint. Binary (or dichotomized) response endpoints will analyzed by CMH test stratified by the prostanoid usage status.

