### 6.3 Handling of Missing Data

#### Missing data imputation for primary endpoint:

For primary analysis, i.e. change from baseline at Week 18, missing data will not be imputed.

The following missing data imputation techniques will be employed for sensitivity analyses of primary endpoint.

- 1) Last Observation Carry Forward (LOCF) approach will be applied for subjects not withdrawing trial due to adverse events, for subjects withdrawing trial due to adverse events (including deaths), worst value (for e.g. zero for 6MWD) will be assigned at 18 weeks visit.
- 2) Worst-case imputation approach I (i.e. impute the missing value for a subject with worst value (within the subject) for all subjects who withdraw prematurely for any reason. The value of zero for 6MWD will be imputed for all deaths.
- 3) Worst-case imputation approach II (i.e., impute the missing value for a subject in the active and Placebo dose group by the worst result of all subjects with non-missing assessments in their respective assigned dose groups). The value of zero for 6MWD will be imputed for all deaths.
- 4) Worst-case imputation approach III (i.e. impute the missing value for a subject in the active dose group by the worst result of all subjects with non-missing assessments in the same active dose groups and impute the missing value for a subject in placebo group by his/her last available assessment prior to the missing assessment. The value of zero for 6MWD will be imputed for all deaths.

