#### 7.1.3 Intent to Treat (ITT) Analysis Set

The ITT analysis set will include all randomized subjects who remained eligible after the Run-in period. It will compare the treatment groups on the basis of randomized treatment rather than treatment actually received.

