Change from baseline in 6MWD for subjects with with PAH SPECIFIC THERAPIES (PHST) [PHST] and algorithm to filter for oral treatments.	MMRM	ITT (all subjects on at least two oral treatment of either prostacyclin or Endothelin Receptor Antagonists (ERAs) or Phosphodies terase Inhibitors	Treatment Group, Visit, Treat*Visit Prostanoid Usage and Baseline 6MWD	Sensitivity	No imputation

Variable	Model	Population	Factors	Primary /Sensitivity	Imputation technique /algorithm
		(PDE 5 Inhibitors)			
Change from baseline in 6MWD ranks analyzed using same model as primary.	MMRM	ITT	Treatment Group, Visit, Treat*Visit Prostanoid Usage and Baseline 6MWD	Sensitivity	No Imputation
Responder for patients achieving $\geq 30$ meters 6MWD from baseline at Week 18	Proportion s test	ITT	Treatment	Sensitivity	NA

For open label period of study change in 6MWD at month 4, 8 and 12 from baseline (week 2) and week 18 will be analysed for all subjects participated in open label and summarized separately for subjects who switched from placebo to active treatment.

Change in 6MWD at week 18, during blinded period, from baseline will be analyse for subjects who completed 6 months and 12 months of study treatment using mITT population.

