### 7.6.7 The Number of Subjects with Unsatisfactory Clinical Response from Baseline to 18 Weeks

The proportions of patient with unsatisfactory clinical response from baseline at Week 18 will be analyzed using Cochran Mantel Haenszel test (Table 33).

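### The 30 m responder analysis leaves out the prostanoid stratum and does not say how ITT subjects without a Week 18 walk are classed

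*SAP*

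**What the plan says.** **The responder analysis.** SAP Table 24 item 13 plans a comparison of the share of subjects gaining 30 m or more at Week 18, which "will be performed using the proportions test on ITT population". The last row of SAP Table 25 ("Responder for patients achieving $\geq 30$ meters 6MWD from baseline at Week 18") lists a proportions test, the ITT population, treatment as the only factor, and 'NA' for imputation. Every other row of Table 25 includes prostanoid usage and either states that there is no imputation or names a rule.

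**Tests for binary outcomes.** Protocol 16.3.3, on tertiary endpoints, says: "Binary (or dichotomized) response endpoints will analyzed by CMH test stratified by the prostanoid usage status". Protocol 16.3.1, on the primary endpoint, says only that the CMH "test (for dichotomized response analysis) may be utilized in the exploratory analyses". In SAP 7.6.7 the proportion with unsatisfactory clinical response "will be analyzed using Cochran Mantel Haenszel test", and Table 33 lists prostanoid usage as a factor. Table 34 does the same for transplantation.

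**Missing data.** SAP 6.3 says: "The following missing data imputation techniques will be employed for sensitivity analyses of primary endpoint". It then lists an LOCF/worst-value rule and three worst-case rules. For each worst-case rule, "The value of zero for 6MWD will be imputed for all deaths". Table 25 attaches these rules to the Week 18 ANCOVA rows, not to the responder row. SAP 7.1.3 says: "The ITT analysis set will include all randomized subjects who remained eligible after the Run-in period". No Week 18 value is required.

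**The concern.** Two things are unsettled. First, allocation is stratified by prostanoid use, and the primary model, its van Elteren fallback and the log-rank test all use that factor. The responder test does not. If prostanoid use predicts response, a pooled test after stratified allocation overstates the variance and becomes conservative.

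Second, an ITT subject with no Week 18 6MWD cannot be called a responder or a non-responder without a rule, and the plan expects 20% drop-out. If the rule is picked after unblinding, that choice can decide what the analysis appears to show. This matters to readers because a responder rate is easily quoted alongside the mean difference.

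**Working it through.** **1. The plan's own figures.** The documents give no rate or power for the responder analysis. The surrounding design reproduces:
- 150 / (1 - 0.20) = 187.5, so 188 randomised, 94 per arm, for 75 evaluable per arm.
- Hwang-Shih-DeCani spending with gamma = -3 at half the information gives one-sided 0.0046 and 0.0229, as stated.
- Simulating the protocol's promising-zone design (zone 30-80%, non-binding futility) at 30 m and SD 75 m gives 71.3%, against the stated figure of about 71%.

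**2. Assumed response rates.** Take normal changes, placebo mean 0 m, difference 30 m and SD 60 m. The difference and SD lie within the protocol's ranges (30-70 m, 50-75 m); the placebo mean is an assumption.
- Placebo: 1 - Φ((30 - 0)/60) = 1 - Φ(0.5) = 30.9%.
- iNO: 1 - Φ((30 - 30)/60) = 50.0%.
- Difference: 19.1 points.

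Power = Φ[(Δ - 1.96·SE0)/SE1], with SE0 pooled and SE1 unpooled. At 75 per arm SE0 = 0.0801 and SE1 = 0.0786, so power = Φ[(0.1915 - 0.1571)/0.0786] = 66.9%. For SD 50 to 75 m at a 30 m difference the range is 81.7% to 48.7%. With placebo mean -17 m (the Phase 2 subgroup value in protocol 5.1) it is 76.5% to 46.6%.

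**3. Effect of stratifying.** 200,000 simulated trials per case, 75 per arm, one-sided 0.025, overall rates as in step 2, CMH without continuity correction. Each cell shows results for a stratum share of 30% / 50%; both shares are assumed.

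| Stratum odds ratio (assumed) | Unstratified power, % | CMH power, % | Change, points | Unstratified error under the null, % |
|---|---|---|---|---|
| 1 | 68.7 / 68.7 | 68.1 / 68.2 | -0.6 / -0.6 | 2.4 / 2.5 |
| 1.5 | 69.1 / 69.2 | 68.4 / 68.5 | -0.7 / -0.6 | 2.4 / 2.5 |
| 2 | 69.4 / 69.4 | 69.0 / 69.2 | -0.4 / -0.3 | 2.4 / 2.4 |
| 3 | 70.1 / 70.1 | 70.3 / 70.5 | +0.2 / +0.4 | 2.2 / 2.3 |
| 5 | 71.2 / 71.0 | 72.9 / 73.2 | +1.7 / +2.2 | 1.9 / 2.0 |

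The CMH error under the null stays at 2.4-2.6% throughout.

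Other assumed rates give larger gains (76 per arm, two equal strata, iNO/placebo):
- 50/32% and 25/11%: 61.8% stratified against 58.7%, a gain of 3.1 points. Stratum odds ratios are (0.50/0.50)/(0.25/0.75) = 3.0 on iNO and (0.32/0.68)/(0.11/0.89) = 3.8 on placebo.
- 60/40% and 20/9%: 59.8% against 52.9%, a gain of 6.9 points. Stratum odds ratios are 6.0 and 6.7.

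**4. Effect of the missing-data rule.** 94 per arm, rates from step 2 among subjects with data. If missing counts as non-response, the rate becomes p × (1 - missing fraction). For 10% placebo and 30% iNO missing: placebo 0.309 × 0.90 = 27.8%, iNO 0.500 × 0.70 = 35.0%, difference 7.2 points.

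| Missing, placebo / iNO (assumed) | Subjects with data: difference, power | Missing = non-responder: rates, difference, power |
|---|---|---|
| 20% / 20% | 19.1 points, 67.0% | 24.7% vs 40.0%, 15.3 points, 61.4% |
| 15% / 25% | 19.1 points, 67.0% | 26.2% vs 37.5%, 11.3 points, 38.1% |
| 10% / 30% | 19.1 points, 66.6% | 27.8% vs 35.0%, 7.2 points, 18.6% |
| 25% / 15% | 19.1 points, 66.7% | 23.1% vs 42.5%, 19.4 points, 81.2% |
| 30% / 10% | 19.1 points, 66.1% | 21.6% vs 45.0%, 23.4 points, 93.2% |

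The rule can move the result in either direction, depending on which arm loses more subjects.

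**The case against.** **Protocol breach.** A reader might infer that the SAP overrides a binding protocol rule. It does not. The sentence requiring stratified CMH stands under tertiary endpoints. The responder analysis is a sensitivity analysis of the primary endpoint, and there the protocol makes CMH optional. This objection stands in full: what remains is an inconsistency.

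**Lost power.** A reader might infer a material loss of power. That needs prostanoid use to predict a 30 m gain strongly, and no document says it does. Protocol 5.1 reports equal 6MWD improvement on oral therapy alone and on prostacyclin combinations, although in a small post hoc subgroup. With a weak stratum, CMH is marginally worse. This objection largely stands.

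**Deaths and drop-outs removed.** A reader might infer that the plan excludes them. Nothing says so. The population is ITT, and a subject without data could equally be read as not having achieved the gain. Subjects who stop study drug are also encouraged to attend through Week 18 (protocol 10.1 and 11), so stopping treatment need not mean missing data. Exclusion is the likely default of a proportions test run on incomplete data, not a written rule. The objection defeats the stronger claim but leaves the gap open.

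**Already covered.** Sensitivity analyses 3 to 6 handle deaths and drop-outs on ITT, and the responder analysis is one of 14 outside the testing hierarchy. That limits the consequence. It does not define the responder classification: SAP 6.3 offers several rules that can disagree. LOCF could make an early improver a responder, while the within-arm worst-case rule would generally not.

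**Conclusion.** The point holds as an inconsistency and an omission of limited consequence. The 30 m responder analysis is the only row of Table 25 without the randomisation stratum, and the SAP gives no reason.

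- **Stratification.** The pooled test is somewhat conservative if prostanoid use is prognostic: its null error falls to about 1.9-2.0% at an assumed odds ratio of 5. Over odds ratios of 1 to 5 the power change is -0.7 to +2.2 points under the main assumptions. It is about 3 points under another set of rates, and near 7 only with odds ratios of 6 or more. The case for CMH is consistency with the allocation and the other binary endpoints, not power.
- **Missing Week 18.** This is the larger half. The size depends on response rates and arm-specific missingness that the documents do not give, and on the response rates in step 2 applying to subjects with data. Under the assumed 10% placebo / 30% iNO missingness, the unstated rule separates 19.1 from 7.2 points.

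The primary conclusion, the gatekeeping order and the type I error are not affected.

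**What to change.** Amend SAP Table 24 item 13 and the last row of Table 25 before unblinding:

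1. Replace the proportions test with a CMH test stratified by prostanoid use, with factors as in Tables 33 and 34. Prostanoid status must be the stratifying variable in the code, so check the variable order under SAP 7.6.7 before reusing it.
2. Replace 'NA' with a rule: ITT subjects who die or have no Week 18 6MWD count as non-responders. For deaths this follows the zero-distance rule in SAP 6.3, since a zero cannot be a 30 m gain.

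The drafting cost is a line or two, with no new data. The statistical cost is that non-responder counting is conservative for drop-outs unrelated to disease or treatment, and lowers power from about 67.0% to 61.4% at equal 20% missing under the assumed rates. The benefit is a defined ITT quantity fixed in advance. If the sponsor prefers another rule, naming it before unblinding would also close the gap.
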